### Primary outcome variables

The primary outcome will be "definite relapse or probable relapse". Definite relapse will be defined as the occurrence of an episode of illness within the 21-day period after antibiotic completion in which the same organism with similar antibiogram is grown, as in the original episode. Probable relapse will be defined as the occurrence of an episode of illness within 21-day period that is diagnosed to be: Clinical diagnosis of bacterial sepsis, in the setting of a sterile blood culture. Part B of the proforma, along with all investigation reports will be mailed to the nodal center, where a Neonatologist who is unconcerned with the rest of the study, will be asked to adjudicate whether the concerned episode is a relapse or not.

Since this is a non-inferiority trial, the analysis will be done both as per protocol and as per intention to treat. Both the analyses will be reported, bearing in mind that the per protocol analysis is actually the more conservative of the two, with less bias towards "no effect".

In the per protocol analysis, the following subjects will be excluded from analysis:

- a) In the 14-day group: patients whose 8th- 14th day of antibiotics could not be completed for any reason (including, but not limited to non-availability of cannula, a fresh episode of sepsis requiring change of antibiotics, withdrawal of consent or unscheduled discharge),
- b) Subjects in either group whose primary outcome could not be assessed due to loss to follow-up or withdrawal of consent.

In the intention-to-treat analysis, all randomized subjects will be analyzed according to the group to which they were randomized, irrespective of compliance or change of antibiotics due to a fresh episode. Subjects in the 7-day group whose primary outcome could not be assessed due to loss to follow-up or

withdrawal of consent will be assumed to have definite relapse and those in the 14-day group to not have relapse.

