## **Randomization**

Those eligible for randomization will be approached for consent for randomization. Parents will be provided Parent Information Sheet for Randomization (Appendix 3) and the details of the Randomized Controlled Trial will be discussed with them. Written informed consent (3 copies) for randomization will be taken from a parent in the presence of a witness (Appendix 4). One copy will be handed to the parent, one will be kept with the investigator and 1 will be kept in the hospital records. Subjects whose parents give consent for randomization will be randomly allocated to one of 2 groups:

Group A: Antibiotics will be stopped at the end of day 7.

Group B: The same antibiotics will be continued for a total of 14 days.

Those who do not satisfy the criteria for randomization and those whose parents do not give consent, will not be randomized and they will be followed up daily until clinical signs remit and will be administered the standard 14 days course of antibiotics.

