#### Intervention

Among neonates who are allocated to group A, antibiotics will be stopped on day 7 of sensitive antibiotics (ie. immediately after randomization).

Among neonates who are randomized to group B, antibiotics will be continued until day 14 (ie for 7 more days after randomization).

If either of the groups develops signs and symptoms of sepsis, these babies will not be discharged, investigations will be done and appropriate antibiotics will be started. Each Centre will administer empirical antibiotics based upon their standard empirical antibiotic policy. No changes in policy will be made for the RCT. The antibiotics shall be stored, prescribed and dispensed as per the recommendations of Neofax essentials, 2014. All study subjects will receive routine care as per guidelines of the concerned centre.

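### The per-protocol set enforces adherence in the 14-day arm only, so the protocol's statement that per protocol is the more conservative analysis is not assured

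*Protocol*

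**What the plan says.** The protocol's section on primary outcome variables plans both a per-protocol and an intention-to-treat (ITT) analysis, "bearing in mind that the per protocol analysis is actually the more conservative of the two". It gives two per-protocol exclusions. Rule (a) applies to the 14-day group alone: infants whose days 8-14 "could not be completed for any reason" are removed, and the listed reasons include "a fresh episode of sepsis requiring change of antibiotics, withdrawal of consent or unscheduled discharge". Rule (b) applies to both groups but covers only outcomes that cannot be assessed. The ITT analysis keeps every infant, "irrespective of compliance or change of antibiotics due to a fresh episode"; for unassessable outcomes, 7-day infants lost to follow-up or "withdrawal of consent will be assumed to have definite relapse and those in the 14-day group to not have relapse".

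Definite relapse is "the occurrence of an episode of illness within the 21-day period after antibiotic completion" with the same organism and a similar antibiogram. Antibiotics finish at different times in the two arms. Under Randomization: "Group A: Antibiotics will be stopped at the end of day 7". Under Intervention, in the other group, "antibiotics will be continued until day 14 (ie for 7 more days after randomization".

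Under Secondary outcomes, outcome 5 counts relapse over 28 and 35 days from randomisation, by ITT only. The SAP says that analysis will be both per protocol and ITT, without that limit, and does not define the per-protocol set.

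**The concern.** A per-protocol analysis protects a non-inferiority conclusion only if it removes the departures that make the arms look alike. Here the departure that does so most directly, a 7-day infant who goes on receiving antibiotics, is left in. Treating and research staff are unblinded (Blinding section), so selective continuation is possible. In the other arm, infants leave the set because of a post-randomisation event that may itself be a relapse.

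The outcome clock adds a second imbalance. The 21 days run over days 0-21 after randomisation in the 7-day arm and days 7-28 in the 14-day arm. An adjudicated relapse in the first week is a primary event in one arm. In the other it precedes the window, and the protocol does not say how either analysis classifies it.

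At stake is whether readers can rely on the per-protocol result as the cautious one, as the protocol tells them to.

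**Working it through.** **Inputs** (protocol, Sample Size Calculation): 350 per arm, 10% event rate, 7-point margin, one-sided 5%, 90% power, 10% loss. Relapse timing and the share of 7-day infants continued are not in the documents; both are assumed over a range.

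**Plan's own figure.** n = (1.645 + 1.282)² × 2 × 0.10 × 0.90 / 0.07² = 314.6, so 315; 315 / 0.90 = 350. It reproduces.

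Throughout, P(declare non-inferiority) = Φ[(0.07 − (p7 − p14)) / SE − 1.645], with SE = √[p7(1 − p7)/n7 + p14(1 − p14)/n14] and n = 315 per arm unless stated. At 10% v 10%, SE = 0.0239 and power = 0.900.

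**1. Continued 7-day infants retained.** The truth is at the margin, 17% v 10%. A share f of the 7-day arm continues and carries the 14-day risk, so the observed p7 = 0.17 − 0.07f.

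| f | p7 | False non-inferiority |
|---|---|---|
| 0 | 17.0% | 5.0% |
| 2% | 16.86% | 5.6% |
| 5% | 16.65% | 6.5% |
| 10% | 16.3% | 8.3% |
| 20% | 15.6% | 13.2% |

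For f = 10%: SE = 0.0268 and Φ[(0.07 − 0.063)/0.0268 − 1.645] = 0.083.

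**2. The window.** No true difference, risk running from randomisation. The hazard is c·exp(−ln2·t/half-life), scaled to 10% risk over days 0-21, with S(t) the proportion still free of relapse. If rule (a) removes every first-week relapse, the 14-day rate is 1 − S(28)/S(7). If those infants are kept but the episode is not counted, it is S(7) − S(28). With a constant hazard, S(7) = 0.96549 and S(28) = 0.86894, giving 10.0% and 9.65%.

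| Hazard | First-week risk | Rule (a): 14-day rate, false excess, power | Kept, not counted: rate, false excess, power |
|---|---|---|---|
| Constant | 3.5% | 10.0%, 0, 0.90 | 9.65%, 0.35, 0.88 |
| Half-life 28 d | 4.1% | 8.5%, 1.5, 0.77 | 8.1%, 1.9, 0.73 |
| Half-life 14 d | 4.7% | 7.2%, 2.8, 0.59 | 6.8%, 3.2, 0.54 |
| Half-life 7 d | 5.8% | 5.1%, 4.9, 0.26 | 4.8%, 5.2, 0.22 |

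The excess is in points, 7-day minus 14-day. It is no smaller when the infants are kept, so the window produces it, not the exclusion. The last column is also what ITT would show, before imputation, if such episodes are not counted. If risk starts when antibiotics stop, both arms have 10% and there is no bias.

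**3. Both together.** 7-day arm at 17%, 14-day arm at the rule (a) rate in step 2, f = 5-20%. False non-inferiority is 6.5-13% (constant hazard), 1.8-5.8% (28 d), 0.5-2.3% (14 d) and below 0.4% (7 d). If risk starts at antibiotic stop, nothing offsets step 1.

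**4. Outcome 5 at 28 days from randomisation.** With risk from randomisation, the 28-day risk is 13.1, 12.2, 11.5 or 10.7% in both arms, and power is 0.83-0.89. Run per protocol with rule (a) unchanged, the 14-day rates are again 10.0, 8.5, 7.2 and 5.1%, a false excess of 3.1, 3.7, 4.3 or 5.5 points (from unrounded rates). If risk starts at antibiotic stop, the comparison is 13.1-10.7% v 10% and power is about 0.45-0.83, because the 7-day arm has seven more antibiotic-free days.

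**5. Symmetric exclusion.** Removing 10% of the 7-day arm leaves 0.9 × 315 ≈ 284. Power is 0.886 and error 5.0% if continued infants resemble the rest. Suppose their underlying risk is k times that of the rest, with the arm at 17% overall. The rest then have 0.17/(0.9 + 0.1k). For k = 2 this is 15.5%, and excluding the continued infants gives an error of 14.0%. Keeping them, with their own risk reduced in the ratio 10/17 by continued treatment, gives p7 = 0.9 × 0.1545 + 0.1 × 0.3091 × 10/17 = 15.7% and an error of 12.2%. For k = 1.5 the errors are 8.8% excluded and 10.2% retained.

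**The case against.** The strongest reply has four parts.

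- **Attribution.** A reader might infer that rule (a) itself creates a false 7-day excess of up to 5 points and cuts power to about a quarter. The documents do not support that. The primary definition already leaves the first week out of the 14-day count, and step 2 shows the excess slightly larger when rule (a) is not applied. This stands.
- **Frequency.** Nothing indicates how often 7-day infants continue, and the Intervention section has antibiotics stopped immediately after randomisation. At 2% the error is only 5.6%. With risk from randomisation, the combined error clearly exceeds 5% only when the hazard is near constant. A reader might therefore go too far in concluding that the per-protocol analysis favours non-inferiority overall; the net direction is unknown. This stands too.
- **Other protection.** ITT is reported alongside, with missing outcomes set against the 7-day arm. At 10% loss, that imputation turns 10% v 10% into 0.9 × 10 + 10 = 19% v 9%, with power of about 0.003 at 350 per arm. It is a real counterweight to false non-inferiority, but it acts through loss to follow-up and does not repair the per-protocol set.
- **Outcome 5 already exists.** By ITT it captures first-week relapses in both arms. True, but it is not planned per protocol, and the SAP sentence does not match the protocol's limit.

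One precision also stands. Rule (a) names episodes that require a change of antibiotics, so an infant who completes the course unchanged stays in. A new organism would be a secondary infection, not a relapse.

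**Conclusion.** The point holds in a limited form and should be fixed. It is certain on the text that adherence is enforced in one arm only and that first-week relapse is a primary event in one arm only. The size is not certain. Retaining continued 7-day infants raises false non-inferiority to 5.6-13.2% for assumed shares of 2-20%, if those infants carry the 14-day risk. The window gives a false 7-day excess of about 0 to 5 points if risk runs from randomisation, and about nil if it starts at antibiotic stop. Because these pull in opposite directions and neither frequency nor timing is documented, the protocol cannot promise that per protocol is the more conservative analysis. The sample size is correct on its own inputs and is not in question.

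**What to change.** 1. **Make the adherence exclusion symmetric.** Also exclude from the per-protocol set 7-day infants whose antibiotics were continued past day 7 for reasons other than a new episode of illness, with the reason classified from records by someone blind to outcome. Report numbers and reasons by arm, and add a sensitivity analysis that retains these infants. Cost: a slightly smaller set (power about 0.89 if 10% are excluded) and possible selection bias if continued infants are at higher risk (14.0% v 12.2% at twice the risk), which is why the sensitivity analysis is needed.

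2. **Run outcome 5 (28 days from randomisation) per protocol as well as ITT**, make the protocol and SAP agree, and report it beside the primary as supportive. In this analysis do not exclude 14-day infants because of a fresh sepsis episode, and count adjudicated relapses from randomisation in both arms; otherwise it carries the 3.1-5.5 point false excess. Rule (a) reaches any reason for non-completion, so this needs an explicit exception. The pair is informative: outcome 5 is free of the timing bias if risk runs from randomisation, and the primary is free of it if risk starts at antibiotic stop.

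3. **For the primary itself, do not keep first-week infants while leaving their episode uncounted**, since that slightly worsens bias and power. Tabulate adjudicated day 8-14 relapses by arm. State how they are classified in the per-protocol and ITT analyses and when the 21-day window starts after a changed course. Follow-up ends 35 days after randomisation, so a course ending later than 35 − 21 = 14 days after randomisation would run past it. Remove or qualify the statement that per protocol is more conservative, and define the set in the SAP.

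Items 1 and 2 cost wording, one extra analysis and a sensitivity run. They need no new outcome data, because the protocol already has illness episodes over 35 days evaluated and adjudicated blind.

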# Inclusion Criteria

Subjects should satisfy all the following criteria:

- Neonates aged 0-28 days, either inborn or out born, who are currently admitted in the Neonatal unit of the centre,
- Whose birth weight is greater than 1000 grams (it should be reliably ascertained from records of a hospital.
- Whose residence is within approximately 15 kms from the centre, so that the infant can be brought back to the centre for follow up.
- Who have suspected septicemia for which a conventional or BACTEC/BACTALERT blood culture is sent and for which the treating physician decides to start antibiotics.

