All episodes of illness in a 35-day period after randomization will be evaluated for antibiotic treatment failure. A blood culture and sepsis screen (C reactive protein, complete blood counts,), procalcitonin, chest X-ray and CSF examination will be done, depending on the discretion of the treating physician. All clinical and laboratory details related to the episode of illness will be recorded on Proforma part B, detached and handed over to a blinded Neonatologist (adjudicator) to determine whether the episode qualifies to be a relapse of sepsis. In case any radiological imaging is performed, either digital (preferable) or hard copies of the images will be sent to the blinded Neonatologist at the nodal Centre after removing patient identifiers. In the event that the subject could not be brought back to the unit for the episode of illness, and treatment was received outside, every effort will be made by the assessment team to contact the treating physician and ascertain all details and such details will be entered in pro forma part B. Photocopies of lab reports and notes of other physicians will also be sent to the blinded neonatologist, after removing patient identifiers. Proforma part B will not contain any information by which the group of randomization may be ascertained.

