### **Sample Size Calculation**

The sample size was calculated to be 350 in each arm based on the following assumptions: Event rate for the composite primary outcome of "definite or probable relapse" assumed to be 10% (combining both 7- and 14-day treatment arms) based on the earlier study (Chaudhary G, Dutta S, Narang A, Journal of Tropical Pediatrics 2006), non-inferiority margin of 7%, one sided alpha level as 5% and power of 90% and loss to follow- up of approximately 10%.

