Title:

Comparison of the Efficacy of a 7-day Versus 14-day Course of Intravenous Antibiotics in the Treatment of Uncomplicated Neonatal Bacterial Sepsis: a Randomized Controlled Noninferiority Trial

NCT number: NCT 03280147

Date of document: 26 September 2019

STATISTICAL ANALYSIS PLAN

The baseline variables shall be described using descriptive statistics. Categorical variables will be described by percentages. Numerical variables will be described as mean (standard deviation) or median (1st, 3rd quartile), depending on distribution. Normality of distribution of numerical variables will be tested by Shapiro Wilk test and QQ plot.

The primary outcome variable is "definite or probable relapse" within 21 days after stopping antibiotics. Secondary outcome variables include individually definite and probable relapse within 21 days and 28 days after stopping antibiotics; definite and probable relapse within 28 days and 35 days after randomization; "definite or probable relapse" within 28 days and 35 days after randomization; secondary bacterial infections within 35 days after randomization and adverse events within 35 days after randomization. Analysis will be both per protocol as well as intention-to-treat, as this is a noninferiority trial.

As all the outcome variables are categorical, chi-square test with Yates correction or Fisher's Exact test, as applicable, will be used to compare the 2 groups.

Sub-group analysis has been planned for the following sub-groups: birth weight 1000-1499 grams, 1500 to 2000 grams, and >2000 grams, those infected with gram positive organisms versus the rest and those with radiological pneumonia versus those without radiological pneumonia. A p-value for the test of interaction (Breslow-Day test) will be derived for the subgroup analyses.

Multi variable logistic regression analysis will be performed to determine the relationship between group membership (7-day course of antibiotics versus 14-day course of antibiotics) and the primary outcome after adjusting for the following baseline covariates: birth weight, age of neonate, infection with gram positive organisms, number of days by which clinical remission of sepsis achieved prior to randomization.

Mid-term analyses will be performed by an independent Data Safety Monitoring Board at 1/3rd and 2/3rd of expected recruitment.

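### The only intention-to-treat analysis scores missing outcomes in opposite directions by arm, so at the planned 10% loss it would almost certainly miss the 7-point margin even if the two courses were equally effective

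*Protocol*

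**What the plan says.** The Protocol, under Primary outcome variables, plans a per-protocol and an ITT analysis and will report both.

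- **ITT.** The principle is that "all randomized subjects will be analyzed according to the group to which they were randomized". Infants in the 7-day arm whose primary outcome is missing through loss to follow-up or "withdrawal of consent will be assumed to have definite relapse and those in the 14-day group to not have relapse". This is the only ITT handling given, and it is not labelled a sensitivity analysis.
- **Per protocol.** Exclusion (b) removes infants with an unassessable primary outcome from both arms. Exclusion (a) also removes 14-day infants who did not complete days 8 to 14, one listed reason being "a fresh episode of sepsis requiring change of antibiotics".
- **How the two compare.** Readers are to take the results "bearing in mind that the per protocol analysis is actually the more conservative of the two, with less bias towards" a finding of no effect.

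Sample Size Calculation gives 350 per arm for 90% power, with a 10% event rate, a 7% margin, one-sided alpha of 5% and "loss to follow- up of approximately 10" per cent. It does not say which analysis the power refers to.

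The SAP repeats that both analyses will be done. It gives no rule for missing outcomes.

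**The concern.** A non-inferiority trial needs an ITT estimate that can be read as a comparison of the two courses. Here every unassessable infant in the 7-day arm adds an event, and every unassessable infant in the 14-day arm adds a non-event. Two equally effective courses will therefore look different by an amount set by follow-up. The sample size, by contrast, appears to treat loss only as a reduction in numbers.

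At stake is whether the ITT result can be interpreted. If it missed the margin, a reader could not tell more relapse after 7 days from incomplete retention. The protocol's guidance on which analysis is stricter would also point the wrong way as far as missing outcomes are concerned.

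**Working it through.** **Inputs.** From Sample Size Calculation: 350 per arm, 10% event rate, 7% margin, one-sided alpha 5%, power 90%, loss about 10%. The margin is read as absolute percentage points, the reading that reproduces 350. Assumed, because the documents do not state it: 10% true relapse in both arms, loss unrelated to outcome, and non-inferiority shown when the one-sided 95% Wald upper bound for the 7-day minus 14-day difference is below 7 points.

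**1. Reproduce the plan's figure.**
n = [0.10×0.90 + 0.10×0.90] × (1.645 + 1.282)² / 0.07² ≈ 315 per arm. Allowing for loss: 315 / 0.9 = 350, an exact match. So 90% power belongs to an analysis of about 315 observed infants per arm.

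**2. Effect of the ITT rule.** With true relapse r7, r14 and loss L7, L14:
- 7-day rate = r7(1 − L7) + L7
- 14-day rate = r14(1 − L14)
- added difference = (1 − r7)L7 + r14·L14, which is never negative

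With r7 = r14 and L7 = L14 = L, the added difference is L.

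**3. Planned 10% loss.** 7-day: 0.10×0.90 + 0.10 = 0.19. 14-day: 0.10×0.90 = 0.09. Difference: 0.10.
SE = √[(0.19×0.81 + 0.09×0.91)/350] = 0.0260.
Chance of meeting the margin ≈ Φ[(0.07 − 0.10)/0.0260 − 1.645] = Φ(−2.80) ≈ 0.3%.

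**4. Other loss rates.** Exact binomial enumeration, 350 per arm. The 1% to 5% rows are illustrations and do not come from the documents.

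| Loss in each arm | 7-day rate | 14-day rate | Artificial difference | Chance ITT meets margin |
|---|---|---|---|---|
| 0% | 10.0% | 10.0% | 0 | 92.5% |
| 1% | 10.9% | 9.9% | 1 point | 83.0% |
| 2% | 11.8% | 9.8% | 2 points | 68.8% |
| 3% | 12.7% | 9.7% | 3 points | 51.7% |
| 5% | 14.5% | 9.5% | 5 points | 20.8% |
| 10% (planned) | 19.0% | 9.0% | 10 points | 0.27% |

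A Newcombe bound changes each figure by less than 1 percentage point. If lost infants are simply left out, power at 10% loss is 90.0%.

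**5. Sensitivity.**
- True relapse: at 3% loss the chance is 70% with 5% relapse and 42% with 15% relapse. With no loss those base rates give 99.5% and 83%, so part of the 42% comes from the base rate. At 10% loss the result stays between 0.1% and 0.4% (normal approximation).
- Unequal loss (7-day/14-day): 0%/10% adds 1.0 point (about 85%); 5%/15% adds 6.0 points (11%); 12%/8% adds 11.6 points (0.04%).

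**6. False claims.** With the truth at the margin (17% against 10%), the chance of wrongly showing non-inferiority is about 5% with no loss, 3.4% at 0%/5% loss and 0.4% at 3%/3%.

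**The case against.** The best defence is that the rule is a deliberate, prespecified worst case standing beside a per-protocol analysis around which the trial was planned. Much of this stands.

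- **Symmetric handling already exists.** Per-protocol exclusion (b) drops missing outcomes in both arms, so it would be wrong to infer that the plan has none. It does not replace a symmetric ITT, because exclusion (a) also removes non-completing infants from the 14-day arm only, and that set may fall below 315.
- **The protocol never claims 90% power for ITT.** A reader might infer a broken promise. Sample Size Calculation is silent on the analysis set, and its arithmetic fits observed outcomes. What remains is that the power does not carry over and the text does not say so.
- **ITT is not stated to be decisive.** A reader might take 0.3% as the trial's chance of success. The documents say only that both analyses will be reported, and give no rule for when they disagree.
- **Loss may be well below 10%.** The residence criterion was set "so that the infant can be brought back to the centre for follow up", home visits are planned, and for illness treated elsewhere "every effort will be made by the assessment team to contact the treating physician". These are real safeguards, but about 10% is the only figure given, and the table shows that small losses matter.
- **Per protocol may still be stricter overall.** Exclusion (a) also moves that estimate, in a direction the documents do not settle. The primary outcome counts episodes after antibiotic completion, so excluding a 14-day infant for a day 8 to 14 episode need not remove a relapse.

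**Conclusion.** The concern holds in a limited form. At the protocol's own planning loss, the sole ITT analysis adds a 10-point artificial difference against a 7-point margin and has about a 0.3% chance of meeting it when the courses are equally effective. This rests on 10% true relapse in both arms, equal loss unrelated to outcome, 350 per arm and a one-sided 95% Wald bound inferred from the sample size section. With unequal loss the size depends mainly on loss in the 7-day arm.

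For missing outcomes, the ITT rule is harsher on the 7-day arm than per protocol at any loss above zero. That does not fit the description of per protocol as the more conservative analysis. Which analysis is stricter overall is not fixed, and no threshold of loss at which the order reverses can be derived from the documents.

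A reader might also infer that the rule endangers the validity of a non-inferiority claim. It does not: the added difference is never negative, so the rule cannot inflate false claims. The cost is an ITT result that reflects retention rather than relapse. It should be fixed, but it does not by itself invalidate the trial.

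**What to change.** 1. Make the main ITT use one missing-data rule in both arms for all randomized infants. One option is multiple imputation using covariates the SAP already names: "birth weight, age of neonate, infection with gram positive organisms, number of days by which clinical remission of sepsis achieved prior to randomization".
2. Keep the present rule as a labelled worst-case or tipping-point sensitivity analysis.
3. State in Sample Size Calculation that the 90% power refers to an analysis of about 315 observed infants per arm.
4. Qualify the sentence calling per protocol more conservative: for missing outcomes the worst-case rule is the harsher one, and the overall order is not fixed.

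The cost is protocol and SAP wording and modest programming, with no new data. The drawback is that the main ITT then rests on a missing-at-random assumption while allocation is open to carers (Protocol, Blinding), so loss could depend on arm. The retained worst case tests that.

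Counting losses as relapse in both arms is a poor substitute. At 10% loss its power is 76%, and its false-claim rate at the margin rises to 7.8%, because the true 7-point difference shrinks to 6.3 points (25.3% against 19%).

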### Secondary outcomes

"Definite relapse" and "probable relapse" will be separate secondary outcomes, each assessed at 21 days and 28 days after antibiotic completion. [This was originally "definite or probable relapse"].

Episodes of relapses (# 1-4) will be analyzed both as per protocol and as per intention-to-treat:

1. "Definite relapse": by 21 days after antibiotic completion.

2. "Probable relapse": by 21 days after antibiotic completion.

3. "Definite relapse": by 28 days after antibiotic completion.

4. "Probable relapse": by 28 days after antibiotic completion.

Episodes of relapses (# 5-7) will be analyzed as per intention-to-treat:

5. "Definite or probable relapse" in the 28-day period after randomization and 35-day period after randomization

6. "Definite" in the 28-day period after randomization and 35-day period after randomization

7. "Probable" in the 28-day period after randomization and 35-day period after randomization]

The following will also be analysed in the 35-day period of observation after randomization:

(A) Episodes of secondary infections during the observation period. These may be bacterial or fungal.

(B) Adverse events: All fresh adverse events occurring after randomisation would be recorded. Adverse events with onset prior to randomisation would be recorded only if there is worsening after randomisation. Adverse events are listed and defined as per Appendix 5.

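### The intention-to-treat rule for lost infants imputes definite relapse in the 7-day arm; carried into the separate relapse outcomes, it would create an excess of culture-proven relapse that no culture showed

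*Protocol*

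**What the plan says.** The ITT rule is in the protocol under Primary outcome variables. It is triggered for "Subjects in the 7-day group whose primary outcome could not be assessed due to loss to follow-up or" withdrawal of consent. Such infants "withdrawal of consent will be assumed to have definite relapse and those in the 14-day group to not have relapse". The same section keeps these infants out of the per-protocol analysis: "Subjects in either group whose primary outcome could not be assessed due to loss to follow-up or withdrawal of consent" are excluded.

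That section also defines the two kinds of relapse. A definite relapse is an episode "in which the same organism with similar antibiogram is grown, as in the original episode". A probable relapse is a "Clinical diagnosis of bacterial sepsis, in the setting of a sterile blood culture". One episode cannot be both.

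Under Secondary outcomes the protocol makes definite and probable relapse separate outcomes and assigns their analysis sets:

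- Outcomes 1 to 4 (each component at 21 and 28 days after antibiotics end): "Episodes of relapses (# 1-4) will be analyzed both as per protocol and as per intention-to-treat".
- Outcomes 5 to 7 (composite, definite and probable at 28 and 35 days after randomisation): "Episodes of relapses (# 5-7) will be analyzed as per intention-to-treat".

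The SAP repeats the split ("Secondary outcome variables include individually definite and probable relapse within 21 days and 28 days after stopping antibiotics"). It calls for both per-protocol and ITT analyses and gives no missing-data rule of its own.

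**The concern.** The rule is meant to be severe on the 7-day course, and for the composite it is: a lost 7-day infant is an event whichever relapse label is used. For the separate components the label decides everything. A lost 7-day infant becomes an event for definite relapse and a non-event for probable relapse. A lost 14-day infant is a non-event for both. The same infants therefore carry opposite missing-data assumptions in two outcomes reported side by side.

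The components are there to show whether any excess after the shorter course is culture-proven or only clinical. If the label is carried over, loss to follow-up would appear as bacteriological failure of the 7-day course. That is the more serious of the two findings, and here it would have no culture behind it.

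**Working it through.** **Inputs.** From the protocol, Sample Size Calculation: 350 per arm, composite rate 10%, margin 7 points, one-sided alpha 5%, power 90%, loss about 10%. From Data analysis: chi-square with Yates correction. Assumed, because the documents give neither: equal loss in the two arms, and a 5%/5% split of the composite into definite and probable (definite rate varied from 2% to 8%).

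**The plan's own figure.** n = (1.645 + 1.282)² × 2 × 0.10 × 0.90 / 0.07² = 314.6, so 315 per arm. Allowing for 10% loss, 315 / 0.9 = 350. The stated size is reproduced.

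**Derived rates under the rule.** Let L be the proportion lost before the primary outcome can be assessed, and d and p the true definite and probable rates, the same in both arms.

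- Definite: 7-day (1 − L)d + L; 14-day (1 − L)d; difference L, whatever d is.
- Probable: (1 − L)p in both arms; difference 0.

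At L = 0.10, 0.10 × 350 = 35 infants are lost per arm. All 35 in the 7-day arm become definite relapses. None in either arm becomes a probable relapse.

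| Outcome, 10% loss, no true difference | 7-day | 14-day | Difference |
|---|---|---|---|
| Definite, true rate 5% | 0.9 × 5 + 10 = 14.5% | 0.9 × 5 = 4.5% | 10 points |
| Definite, true rate 2% | 11.8% | 1.8% | 10 points |
| Definite, true rate 8% | 17.2% | 7.2% | 10 points |
| Probable, true rate 5% | 4.5% | 4.5% | 0 |

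**How often the planned test would call definite relapse different** (Yates chi-square, two-sided 5%, 350 per arm, two independent binomials at the derived rates, no true difference):

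| Loss | True rate 5% | True rates 8% to 2% |
|---|---|---|
| 3% | 31% | 24% to 51% |
| 5% | 68% | 55% to 89% |
| 10% | 99.5% | 98% to more than 99.9% |

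**Probable relapse with a real difference.** Suppose the true rates are 12% v 5% (illustrative). The derived rates are 0.9 × 12 = 10.8% and 0.9 × 5 = 4.5%, so 7.0 points become 6.3. The factor of 0.9 is the most that 10% loss can do, because it assumes that no relapse was recorded before the infant was lost. The Yates test rejects in about 86% of trials with these rates and 350 per arm. It also rejects in about 86% when only assessed infants are analysed (12% v 5%, 315 per arm). The dilution costs no power against that alternative.

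**Later windows.** The trigger is the primary outcome, 21 days after antibiotics end. For a 7-day infant that is day 21 after randomisation; for a 14-day infant it is day 7 + 21 = 28. A 7-day infant lost on day 25 has an assessable primary outcome, so the rule does not apply, yet the 28-day and 35-day outcomes are incomplete. Neither document says how to count that infant.

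**The case against.** The strongest reply is that carry-over is an inference. The rule stands under the primary outcome and is worded for a missing primary outcome, and no sentence in either document extends it to the components. That is correct, and a reader should not infer that the plan prescribes the artefact. But the protocol sends the components to ITT and describes that analysis in only one place. A programmer following the text would either use this rule or have none. Both readings need the same repair.

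Other objections also stand in part:

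- A 10-point gap is what any one-sided worst case produces at 10% loss, so it is not peculiar to the label. The composite under the same rule moves from 10% v 10% to 19% v 9%. For the composite, however, that is a declared conservative choice; for definite relapse it would read as culture-proven failure. Applying the worst case to each component in turn would not help: probable relapse would then also become 14.5% v 4.5%.
- The per-protocol analyses of outcomes 1 to 4 exclude these infants, so an analysis without imputation is already planned there. It also drops 14-day infants who did not complete treatment, so it is not simply an analysis of assessed infants. The protocol gives outcomes 5 to 7 ITT only, although the SAP's general statement could be read as covering them.
- The 10% loss is a planning allowance. The residence limit and home visits are meant to keep loss lower, and the components have no margin or power claim of their own.

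It is also tempting to say that infants lost after the primary window are counted as relapse-free. The documents do not say so; their handling is unstated.

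**Conclusion.** The concern holds for the ITT analyses of the separate components, on the condition that the primary-outcome rule is applied to them as written. The serious effect is on definite relapse: a false excess equal to the loss rate, 10 points at the planned loss, whatever the true rate. The figures of 14.5% v 4.5% and the rejection rates of 99.5%, 68% and 31% rest on an assumed 5% definite rate and equal loss in both arms. The conclusion does not change over definite rates of 2% to 8%.

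Two stronger readings are not supported. A reader might infer that a real excess of probable relapse would be hidden; the shrinkage is at most a factor of 0.9 at 10% loss and costs no power against an analysis of assessed infants. A reader might also infer that the choice of label affects the primary result; it does not, because either label makes the infant an event for the composite. This is a defect in secondary results, worth correcting before analysis because it could put a misleading bacteriological finding in the report.

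**What to change.** In the protocol's ITT paragraph and in the SAP, state that the imputation applies only to the composite of definite or probable relapse by 21 days after antibiotics end. For the separate definite and probable outcomes (1 to 4, 6 and 7), make the main analysis one of these:

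- infants assessed for that outcome's own window, in the arm to which they were randomised; or
- multiple imputation by arm, using the randomisation stratum and baseline covariates.

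Judging missingness on each outcome's own window also settles the infants lost between the primary and later windows. If a worst case for each component is wanted, label it a sensitivity analysis only.

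The cost is about two sentences, with no change to treatment, data collection or the primary result. There are two small downsides. The component results will no longer sum exactly to the imputed composite. The assessed-infant option also departs from the protocol's statement that ITT covers everyone randomised, so the SAP should name that analysis set explicitly.
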